7.3.2 Handling of missing or incomplete dates

Imputation rules for missing or partial AE start dates are defined below:

If only Day of AE start date is missing:

If the AE start year and month are the same as that for the first dose date, then:

- If the full (or partial) AE end date is NOT before the first dose date or AE end date is missing, then impute the AE start day as the day of first dose date;
- Otherwise, impute the AE start day as 1.

If Day and Month of AE start date are missing:

If AE start year = first dose year, then:

- If the full (or partial) AE end date is NOT before the first dose date or AE end date is missing, then impute the AE start Month and Day as the Month and Day of first dose date
- Otherwise, impute the AE start MONTH as January and the DAY as 1.

If Year of AE start date is missing:

If the year of AE start is missing or AE start date is completely missing, then query site and leave as missing.

For missing and partial adverse event end dates, imputation will be performed as follows:

If only the day of the month is missing, the last day of the month will be used to replace the missing day. If the day and month are missing or a date is completely missing, it will be considered as missing.

Imputation rules for missing or partial medication start/stop dates are defined below:

If only Day of CM start date is missing:

If the CM start year and month are the same as that for the first dose date, then:

- If the full (or partial) CM end date is NOT before the first dose date or CM end date is missing, then impute the CM start day as the day of first dose date;
- Otherwise, impute the CM start day as 1.

If Day and Month of CM start date are missing:

If CM start year = first dose year, then:

- If the full (or partial) CM end date is NOT before the first dose date or CM end date is missing, then impute the CM start Month and Day as the Month and Day of first dose date
- Otherwise, impute the CM start MONTH as January and the DAY as 1.

If Year of CM start date is missing:

If the year of CM start is missing or CM start date is completely missing, then query site and leave as missing.

8 STATISTICAL METHODS

8.1 General statistical conventions

All statistical procedures will be completed using SAS version 9.3 or higher.

Unless otherwise stated, all statistical testing will be two-sided and will be performed using a significance (alpha) level of 0.05. Two-sided 95 % confidence intervals (CI) will be provided when relevant. Any p-value below 0.05 will be displayed to 4 decimal places.

Any p-value less than 0.0001 will be displayed as <0.0001. Any p-value between 0.05 (inclusive) and 0.10 will be displayed to 3 decimal places and any p-value greater than 0.10 will be displayed to two decimal places. Any p-value greater than 0.9999 will be displayed as >0.9999.

All quantitative endpoints will be summarized using an 8-number summary (n, mean, standard deviation, median, 25th percentile, 75th percentile, minimum and maximum values). The mean and median and the percentiles will be rounded to one decimal place beyond the precision of the values being summarized, the standard deviation will be rounded to 2 additional decimal places beyond this precision and the minimum and maximum values will be displayed in the same precision. All qualitative endpoints will be summarized by the number of subjects meeting the endpoint and the percentage of subjects out of the appropriate population. The denominator will be displayed when needed and the percentage will be rounded to one decimal place

All subject data, including those derived, will be presented in individual subject data listings. Unless otherwise stated, unscheduled visit results will be included in date/time chronological order, within subject listings only. All listings will be sorted by investigational site, patient number, date/time and visit. The treatment group as well as patient's sex and age will be stated on each listing. Unless otherwise stated, data listings will be based on all subjects randomized.

Descriptive statistics in tables will include a pooled EDP-305 group (Combined EDP-305) except PK information. No inferential analysis will be performed using the combined group. No figures or listings will include the combined group. The overall (totals) will only be presented for study disposition.

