10.2. Management of Liver Enzyme Elevations

The FDA Guidance for Industry for Drug Induced Liver Injury (*FDA*, 2009) will provide guidance for the management of changes in liver transaminases (ALT/AST) and total bilirubin.

The following close observation guidelines will apply to subjects for whom the repeat assessment shows persistent elevations of transaminases, but who do not meet drug discontinuation criteria, and for subjects who discontinue study drug due to ALT/AST elevations.

The protocol also includes an algorithm to respond to changes in liver enzymes and functions as follow:

- To establish a baseline utilizing at least 2 lab values at least several weeks apart
- For subjects with elevated baseline liver chemistry that develop AST or ALT elevations $2 \times$ baseline, subjects will be reassessed promptly (eg, 48–72 hours) with full liver biochemistry and physical exam and if the repeat assessment shows persistent elevations in transaminases, subjects should be followed according to the “close observation” guidelines:
 - Repeat liver enzyme and serum bilirubin tests two or three times weekly. Frequency of repeat testing can decrease to once a week or less if

- abnormalities stabilize or the trial drug has been discontinued and the subject is asymptomatic.
- Collect additional PK samples at the same visits as safety labs
 - Obtain a more detailed history of symptoms and prior or concurrent diseases.
 - Obtain a history of concomitant drug use (including nonprescription medications and herbal and dietary supplement preparations), alcohol use, recreational drug use, and special diets.
 - Rule out acute viral hepatitis types A, B, C, D, and E; autoimmune or alcoholic hepatitis; NASH; hypoxic/ischemic hepatopathy; and biliary tract disease.
 - Obtain a history of exposure to environmental chemical agents.
 - Obtain additional tests to evaluate liver function, as appropriate (eg, INR, direct bilirubin).
 - Consider gastroenterology or hepatology consultations.
 - Consider liver biopsy for any patient with persistent evidence of liver injury.
- For subjects with alkaline phosphatase (ALP) elevations of $2 \times$ ULN, subjects will be reassessed promptly (eg, 48–72 hours) with full liver biochemistry and physical exam. Labs should be repeated until resolution. Above guidelines for close monitoring should also apply.
 - If a subject lives in a remote area, they can be tested locally with the results promptly communicated to the Investigator site

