8.7.2 Stopping Rules

Summaries will be provided using counts and percentages for subjects who meets the stopping rules as described below:

- ALT or AST > 5 x Baseline
- ALT or AST > 2 x Baseline AND concomitant total bilirubin > 2 x Baseline OR Concomitant INR > 0.2 from Baseline
- ALT or AST > Baseline AND Right Upper Quadrant Abdominal Pain, Anorexia, Nausea, Vomiting, Fever, Eosinophilia, and/or Rash

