8.7.2.1 Close Monitoring for Drug Discontinuation due to Elevated ALT/AST

The following close observation guidelines applies to subjects that repeat assessments show persistent elevations of transaminases, but who do not meet drug discontinuation criteria, and for subjects who discontinue study drug due to ALT/AST elevations.

A listing will be used to track and evaluate subjects that are part of the close observation guidelines. Monitoring of these subjects will be ongoing throughout the study.

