8.7.3 Clinical laboratory evaluations

Summaries of clinical laboratory results will be performed using an 8-number summary by visit and treatment. All subjects in the safety population will be included in these summaries. Baseline is defined as the last value collected prior to first dose of study drug.

The number and percentage of subjects with treatment-emergent laboratory abnormalities within 7 days of last dose of study drug will be summarized by treatment group. In addition, shift from Baseline tables will be generated by visit and treatment group. All summary tables will be repeated for abnormalities that occur during the treatment-free follow-up which is defined as occurring more than 7 days after the date of last dose. The denominator for these will include any subject who entered into the 4 week treatment-free follow-up phase.

All laboratory data will be included in the data listings and all test values outside the normal range will be flagged.

Pregnancy test and FSH will be listed separately.

The laboratory parameters listed in Table 2 on the following page will be assessed for each patient.

Creatinine clearance will be calculated by the central laboratory using the Cockcroft Gault equation and actual body weight:

$$CLCr \text{ (mL/min)} = \{((140 - \text{Age [years]}) \times \text{weight[kg]}) / (72 \times \text{SCr[mg/dL]})\} \times 0.85 \text{ (if female)}.$$

where SCr =serum creatinine

Online calculator can be found at:

https://www.kidney.org/professionals/KDOQI/gfr_calculatorCoc

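### SAP 8.1 keeps unscheduled results out of tables by default, so the stopping-rule table can undercount and its INR limb cannot be counted on treatment

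*SAP*

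**What the plan says.** SAP 8.1 (General statistical conventions) sets the default: "Unless otherwise stated, unscheduled visit results will be included in date/time chronological order, within subject listings only".

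The sections that use liver tests do not depart from it:

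- SAP 8.7.2: "Summaries will be provided using counts and percentages for subjects who meets the stopping rules as described below". One limb of the second rule reads "Concomitant INR > 0.2 from Baseline".
- SAP 8.7.3: "The number and percentage of subjects with treatment-emergent laboratory abnormalities within 7 days of last dose of study drug will be summarized by treatment group". It also plans shift tables by visit and treatment group.
- SAP 8.7.2.1: "A listing will be used to track and evaluate subjects that are part of the close observation guidelines". No table is planned for these subjects.

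Protocol 10.2 generates the extra samples. When ALT or AST reaches twice baseline, "subjects will be reassessed promptly (eg, 48–72 hours) with full liver biochemistry and physical exam". If the elevation persists: "Repeat liver enzyme and serum bilirubin tests two or three times weekly". Further tests, with INR as an example, are obtained as appropriate, and subjects in remote areas may be tested locally.

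The Schedule of Assessments (Protocol Table 19, repeated in SAP 3.3) lists none of these draws. It places safety chemistry on Day 3 and Weeks 2, 4, 8 and 12 of treatment, and PT/PTT and INR at Screening and EOS only.

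**The concern.** The stopping-rule table is the only planned output that counts subjects by the liver rule they met, by treatment group. The samples most likely to show that a rule has been met are those taken because a liver signal has appeared, and the default in SAP 8.1 sends exactly those samples to listings. Any resulting error in the table can only be downward, and it falls on subjects with a signal. A reader comparing hepatic findings between doses would be using a count that may exclude subjects taken off drug under the rule being counted.

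**Working it through.** No stated figure is in dispute. The check sets the sections side by side and adds schedule arithmetic.

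**1. Is there an exception to SAP 8.1?** Sections 8.7.2, 8.7.2.1 and 8.7.3 do not mention unscheduled results. The default therefore applies to all three.

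**2. Are the repeat tests unscheduled?** Scheduled post-baseline chemistry on treatment falls on Days 3, 14, 28, 56 and 84, which is 5 draws. The gaps, counted from Day 1, are 2, 11, 14, 28 and 28 days. At full close-observation frequency, one 28-day gap adds 2 × 4 = 8 to 3 × 4 = 12 draws, against 1 scheduled draw. This is an upper range, because Protocol 10.2 lets testing fall to weekly or less once abnormalities stabilize, or once drug is stopped and the subject is asymptomatic.

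**3. Can the INR limb be met from scheduled data?** Scheduled on-treatment INR draws number 0. The early EOT visit repeats the Week 12 procedures, which do not include INR. The only scheduled post-baseline INR is at EOS, Day 112, which is 112 − 84 = 28 days after the last planned dose. Under SAP 8.1 the limb cannot be counted on treatment for any subject. This result needs no assumed event rate.

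**4. Who is lost from the ALT/AST limbs?** Protocol 10.1 and SAP 8.7.2 require no confirmation, so a subject who meets a rule on a scheduled draw is counted whatever the repeat shows. The loss is confined to subjects who meet a rule only on an unscheduled sample. A hypothetical case: ALT is 2.5 × baseline on Day 28 and 5.5 × at the repeat on Day 31, drug is stopped, and ALT is 3 × at EOT. The scheduled values are 2.5 × and 3 ×, so the subject is not counted under the >5 × rule.

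**5. What is lost from SAP 8.7.3?** A subject already abnormal on a scheduled draw remains counted. What can be missed is the worst value, and any abnormality seen only between visits.

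**6. Do the SAP 7.2 windows settle it?** They assign laboratory values by relative day and run without a break from Day 5 to end of treatment + 7. Repeats 2 to 3 days after Days 3, 14, 28, 56 and 84 fall on Days 5–6, 16–17, 30–31, 58–59 and 86–87, in the Week 2, 2, 4, 8 and 12 windows respectively. They could be absorbed, but SAP 7.2 does not say that unscheduled values enter, or which value is used when a window holds several.

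**7. Size.** The documents give neither a hepatic event rate nor the share of events met only on unscheduled samples, so the undercount cannot be computed. Each omitted subject is 1/50 = 2 percentage points in an active arm and 1/25 = 4 points in placebo, at the planned arm sizes. As an illustration of schedule coverage only, suppose an excursion above a threshold lasts d days and starts uniformly within a 28-day gap. It then overlaps a scheduled draw with probability d/28: 11%, 25%, 50% and 75% for d = 3, 7, 14 and 21. The durations are assumptions, and these figures do not estimate the undercount.

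**The case against.** The strongest counter-argument is that SAP 8.1 yields where something else is stated, and SAP 7.2 can be read as stating it. Laboratory values are windowed by relative day, the Day 31 repeat in the example lies in the Week 4 window (Days 22–42), and the two tables count subjects rather than visits. The table shells are in a separate document and might resolve the matter. This shows that a programmer could include the values. It does not show that the SAP tells the programmer to: SAP 7.2 is silent on unscheduled results, while SAP 8.1 addresses them directly.

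A second argument is that these subjects appear elsewhere. Protocol 8.4 has clinically significant laboratory findings recorded as AEs, Protocol 7.2.2 puts an abnormal value that causes withdrawal on the AE form, and disposition and listings add to this. That stands, and it limits the harm. But AE recording of a laboratory finding depends on the investigator's opinion, the discontinuation reasons in Protocol 7.2.1 have no stopping-rule category, and a listing gives no rate by dose.

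Four stronger readings are tempting and are not supported:

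- *That an undercount is certain.* It arises only if some subject meets a criterion on an unscheduled sample alone.
- *That the primary safety endpoint is affected.* That endpoint is the frequency of AEs, SAEs and AEs leading to discontinuation, which SAP 8.1 does not govern.
- *That a dose difference is masked.* If the same fraction were lost in every arm, the ratio between arms would be unchanged and only the absolute difference would shrink. The documents do not show that the fraction differs by arm.
- *That repeat ECGs have the same problem.* Protocol 8.3.1 requires a repeat when the QTcF change exceeds 60 msec or QTcF exceeds 500 msec, and SAP 8.7.6 counts the same thresholds. A scheduled ECG that triggers a mandatory repeat is already counted.

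**Conclusion.** The point holds in a conditional form. With SAP 8.1 applied as written, the stopping-rule table can undercount, and the laboratory-abnormality and shift tables can miss worst values and between-visit abnormalities. The INR limb is the firm part: on treatment it cannot be counted for any subject from scheduled data. The size of the remaining loss is unknown. The conclusion rests on reading SAP 8.1 as governing wherever no exception is stated, and on the unseen table shells not supplying one. At minimum, SAP 8.1 and 7.2 leave a choice that changes a safety count, and that choice should be fixed before unblinding. This point takes no view on the clinical stopping rules.

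**What to change.** Add to SAP 8.7.2 and 8.7.3: *All post-baseline results, scheduled and unscheduled, including local-laboratory results where available, determine whether a subject met a stopping rule or had a treatment-emergent abnormality, and feed a shift table to the worst post-baseline value. By-visit summaries use scheduled visits only.*

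Reconcile SAP 7.2 with this by saying whether unscheduled values enter the windows and which value is used when several fall in one window.

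The cost is a worst-value derivation, possible database entry of local-laboratory results, and a footnote that subjects sampled more often have more chances to show a peak. The INR limb then becomes countable only for subjects in whom an on-treatment INR was drawn, so the table should report that number. No clinical stopping rule and no assessment schedule changes.

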8.2 Subject disposition

All subjects who provided informed consent will be included in a summary of subject accountability. The number and percentage of subjects screened, randomized, and treated, randomized and not treated, as well as the number and percentage of subjects in each analysis population (safety, efficacy, per protocol, and PK) will be summarized. The denominator for the calculation of percentages will be from the number of subjects randomized.

The following categories will also be summarized for subject disposition by treatment group and overall:

- Completed study drug per protocol

- Discontinued study drug early and the primary reason for discontinuation
- Completed the study
- Discontinued from the study early and the main reason for discontinuation

The denominator used for the calculation of percentages will be the number of subjects randomized.

In addition, the number of subjects excluded from Safety, Efficacy and PK analysis sets and reasons for exclusion will be summarized by treatment group and overall.

8.3 Protocol violations/deviations

All protocol deviations identified will be summarized by treatment group and overall, all protocol deviations will be listed.

Summaries will be conducted on all subjects that were randomized.

8.4 Demographics and baseline characteristics

No statistical testing will be performed for the comparison between treatment groups on demographics and Baseline characteristics.

8.4.1 Demographics

Subject demographics will be summarized by randomized treatment group for all subjects in the safety population. Age, height, weight and BMI at Baseline will be summarized using an 8-number summary (n, mean, standard deviation, median, 25th percentile, 75th percentile, minimum and maximum values). Qualitative variables such as gender, ethnicity and race will be summarized using count and percentage.

A by-subject listing will be provided.

8.4.2 Baseline and disease characteristics

The categorical Baseline characteristics such as Baseline ECG and other Baseline lab parameters will be summarized using frequency counts for the safety population. NASH relevant comorbidities, and concomitant medications in the past 6 months will also be summarized.

A summary of NASH diagnosis will be provided for the safety population.

The following are summarized using count and percentage:

- Liver Biopsy \leq 24 mths of screening consistent with NASH **AND** Elevated ALT defined as $50 \leq$ ALT (IU/L) \leq 200 at Screening **AND** MRI-PDFF with $>8\%$ steatosis

OR

- Type II Diabetes Mellitus / Pre-Diabetes defined as Glucose >200mg/dL or fasting glucose >126mg/dL and HB1AC at least 6% **AND** Elevated ALT at Screening, where elevated ALT is defined as $50 \leq \text{ALT (IU/L)} \leq 200$ **AND** MRI-PDFF with >8% steatosis.

Subjects will be considered diagnosed with NASH based on a liver biopsy within the last 24 months, prior to the present study. Otherwise, it will be assumed that subjects were diagnosed as having NASH by phenotype.

A by-subject listing will be provided.

8.4.3 Medical history

A summary of medical and surgical history will be presented by system organ class (SOC) and preferred term (PT) using Medical Dictionary for Regulatory Affairs® (MedDRA) Version 19.0 or higher for the safety population.

A by-subject listing will be provided.

8.4.4 Prior and concomitant medications

Medications used in this study will be coded by using the latest available version of the World Health Organization Drug Dictionary Enhanced (WHODDE).

Prior medications: are defined as those medications with a start date prior to the first dose of study drug.

Concomitant medications: are defined as those medications with a start date on or after the first dose of study drug and within 30 days after the last dose. A medication which started prior to dosing and continued after dosing will also be considered as concomitant medications.

Concomitant medications will be summarized descriptively using frequency tables by anatomical therapeutic chemical (ATC) class and preferred name by treatment group on the safety population. Concomitant diabetes medications will be summarized using the same format.

A by-subject listing will be provided for prior and concomitant medications.

Details for imputing missing or partial start and/or stop dates of medication are described in Section 7.2.2.

8.5 Extent of exposure

8.5.1 Treatment duration

Duration of study drug (in days) will be calculated as: last dose date – first dose date + 1 day, regardless of study drug interruption.

Study drug exposure will be summarised by treatment group on the Safety Population using descriptive statistics. A categorical (0-2 Weeks, 2-4 Weeks, 4-6 Weeks, 6-8 Weeks, 8-10 Weeks, 10-12 Weeks 12-16) summary will be provided.

8.5.2 Treatment compliance

Study drug compliance based on the number of tablets taken will be calculated as:
 $100 \times [(total\ number\ of\ tablets\ dispensed) - (total\ number\ of\ tablets\ returned)] / (total\ number\ of\ tablets\ planned\ to\ be\ taken\ per\ day \times duration\ of\ study\ drug\ exposure\ in\ days)$.
The maximum percentage of tablets taken will be 100%.

Study drug compliance based on study drug exposure will be calculated as:
 $100 \times [1 - (total\ number\ of\ days\ of\ any\ study\ drug\ interruption) / (duration\ of\ study\ drug\ exposure\ in\ days)]$.

Study drug compliance will be summarized by treatment group using 8-number summary. They will also be summarized in categories “<80%, 80% - <90%, 90% - <100% and “≥100% compliant” using frequency tables.

Study drug compliance summaries will be based on the Safety Population.

8.6 Efficacy analyses

This section addresses separately the analyses to be conducted on the primary, secondary, and additional efficacy variables. All the efficacy analyses will be performed using efficacy population as primary analysis.

8.6.1 Analysis methods

Analysis of Covariance (ANCOVA) Model for Change from Baseline

In summaries of efficacy endpoints examining changes from Baseline at Week 12, ANCOVA of the differences between post-Baseline and Baseline measurements will be performed, with treatment group as fixed effects and the Baseline measurement as a covariate.

The model will be used to derive least squares estimates of the treatment differences (each active treatment group versus placebo) in mean change and two-sided 95% confidence intervals. Where applicable, t-statistics corresponding to the type III sums of squares for the differences in the least squares means will be used to obtain p-values for treatment group comparisons (each active treatment group versus placebo). Moreover, two-sided 95% confidence intervals for the mean change within each treatment group will be calculated.

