11.5. Efficacy Endpoints

11.6. Primary Efficacy Endpoints

The primary efficacy endpoint of the study is the change from baseline in ALT at Week 12. All subjects in the efficacy population will be included. Comparisons of treatment arms will be performed using an analysis of covariance (ANCOVA) model with treatment and baseline values included in the model where appropriate. Multiple Imputation (MI) will be used to impute missing data. Details will be provided in the SAP.

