3.2 Randomization and blinding

3.2.1 Randomization

Subjects will be randomized to study treatment using an Interactive Web Response System (IWRS). Subjects will be stratified initially by prior liver biopsy vs no prior liver biopsy. Subjects will be randomized to the treatment groups shown below:

- Treatment Group 1 (N=50); EDP-305 1 mg orally for 12 weeks
- Treatment Group 2 (N=50); EDP-305 2.5 mg orally for 12 weeks

- Treatment Group 3 (N=25); Placebo (PBO) orally for 12 weeks

A minimum of 10 subjects per treatment group will be included in the PK/PD substudy. The randomization code will be produced by Enanta (or designee). The Enanta unblinded biostatistician or designee will review and approve the final randomization list.

During the Screening period, subjects will be identified by a unique screening number assigned by the clinical site. Subjects who have completed screening assessments and are eligible for participation in the study will be randomized before the first dose of study drug (Day -1 or Day 1) and assigned a unique subject number which will be used to identify the subject throughout the study.

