5 SAMPLE SIZE AND POWER

Group sample sizes of 44 (in each dose group) and 22 placebo subjects achieves 80.438% power to reject the null hypothesis of equal means when the population mean difference in ALT is $(-40.0) - (-10.0) = -30.0$ with a standard deviation for both groups of 40.0 and with a significance level (alpha) of 0.050 using a two-sided two-sample equal-variance t-test. To account for a 10% discontinuation rate, 15 additional subjects will be enrolled to attempt to have at least 110 subjects who complete treatment bringing the total number of subjects enrolled to 125.

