The second step of MI analyzes the m sets of data separately using Proc Mixed to estimate the relevant standard errors and least square means. At the end of the second step, m sets of parameter estimates are obtained from separate analyses of m data sets.

Step 3: Combining Results

The third step of MI combines the m estimates into one using PROC MIANALYZE.

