8.6.2 Analysis of primary efficacy endpoint(s)

The primary efficacy endpoint of the study is the change from Baseline in ALT at Week 12. All subjects in the efficacy population will be included, with a secondary analysis

performed on the per protocol population.

Baseline in ALT will be derived based on three different methods (see Table 3): Baseline (Average), Baseline (Last value pre-dose), and Baseline (Screening).

A descriptive summary table will be presented for ALT values, change from Baseline and percentage change from Baseline in ALT by treatment group and visit using the 8-number summary. Percent change from baseline will be analyzed similarly as the change results.

Change from Baseline in ALT at Week 12 will be analysed using an ANCOVA model with treatment as a fixed effect and the associated Baseline value as a covariate. Least squares means and standard errors will be presented for each visit, p-value and 2-sided 95% confidence interval for treatment differences will be presented for each visit. Significance tests will be based on least-squares means using a two-sided $\alpha = 0.05$. As an additional analysis, the primary endpoint will be analysed using the Multiple Imputation method as described in section 7.2.1.

A by-subject listing will be provided for observed and derived variables.

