8.6.4.2 Subgroup Analyses

Subgroup analyses will be performed on selected outcomes in subgroups of interest. All subgroup analyses will be exploratory in nature. As the interest will be on how different treatment regimens work in a specific subgroup, instead of whether the treatment differences are the same across different subgroups, the subgroup analyses will be performed by analyzing the outcome data in different subgroups, instead of analyzing the outcome data in the whole population with subgroup factors included in the analyses model.

Subgroup analyses will be performed for the primary endpoint and the secondary endpoints to determine whether significant differences exist in primary and secondary endpoint results between subgroups.

These subgroup analyses will be carried out using the subjects from the efficacy population.

The list of potential subgroups (with applicable definitions in parentheses) includes the following:

- MRE Week 12 response: (<15% reduction vs \geq 15% reduction in percentage of change from baseline)
- MRI-PDF Week 12 response: (<30% reduction vs \geq 30% reduction in percentage of change from baseline)
- Both MRE Week 12 response (\geq 15% reduction in percentage of change from baseline) and MRI-PDF Week 12 response (\geq 30% reduction in percentage of change from baseline) vs non-response
- NASH Diagnosis (biopsy vs phenotype)
- ALT Week 12 Category (\geq 0 change from baseline
 - (0--10] change from baseline
 - (-10--20] change from baseline
 - (-20--30] change from baseline
 - (-30--40] change from baseline
 - <-40 change from baseline) AND same ALT categories for percent change from baseline

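### Randomisation is stratified by prior liver biopsy, but the primary ALT ANCOVA leaves the stratum out; adding it costs one degree of freedom and corrects an over-wide standard error if biopsy status is prognostic.

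*SAP*

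**What the plan says.** SAP 3.2.1 describes the randomisation: "Subjects will be stratified initially by prior liver biopsy vs no prior liver biopsy". The matching text in Protocol 5.6 is partly redacted, so the stratification rests on the SAP wording alone.

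The analysis models do not carry the factor:

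- SAP 8.6.1, the general efficacy ANCOVA: "with treatment group as fixed effects and the Baseline measurement as a covariate".
- SAP 8.6.2, on the primary endpoint (Week 12 ALT change), says that it "will be analysed using an ANCOVA model with treatment as a fixed effect and the associated Baseline value as a covariate".
- Protocol 11.6: an ANCOVA "model with treatment and baseline values included in the model where appropriate". Protocol 11.6.1 repeats this for the secondary endpoints.
- SAP 8.6.3 and 8.6.4.1 use treatment and baseline throughout. The one model with a further factor, in 8.6.3.1, adds liver-fat response and not the stratum.
- SAP 7.3.1, the multiple-imputation analysis, "analyzes the m sets of data separately using Proc Mixed" and names no stratum term.

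Biopsy status does enter SAP 8.6.4.2 as an exploratory subgroup (biopsy versus phenotype). Those analyses are run within each subgroup, "instead of analyzing the outcome data in the whole population with subgroup factors included in the analyses model". SAP 9, on changes from the protocol, does not discuss the omission.

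**The concern.** Stratified allocation makes the arms nearly balanced on biopsy status, so the treatment estimate already varies less from trial to trial. A model without the stratum does not know this. It leaves the between-stratum variation in the residual and reports a standard error that is too large. What is lost is in the reported standard error, the confidence interval and the p-value; the point estimate itself is hardly affected.

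This is worth attention because about 22 evaluable placebo subjects (25 randomised) carry both dose-versus-placebo comparisons, and planned power is only just above 80%.

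The subgroup analysis does not fill the gap. It leaves the main standard error unchanged, and it uses a derived label. SAP 8.4.2 says: "Subjects will be considered diagnosed with NASH based on a liver biopsy within the last 24 months, prior to the present study". A biopsy within 24 months need not coincide with the any-prior-biopsy factor used at randomisation.

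**Working it through.** **Inputs from the documents (SAP 5, SAP 3.1).** 44 subjects per dose and 22 on placebo (110 in total); difference in ALT change 30 IU/L; SD 40; two-sided alpha 0.05; allocation 2:2:1.

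**Assumptions, not in the documents.** The share R² of post-baseline residual variance explained by the stratum; the stratum split; blocks of 5 within strata; SD 40 taken as the SD after baseline adjustment.

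**1. The plan's own figure.** SAP 5 obtains its power "using a two-sided two-sample equal-variance t-test".

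SE = 40 × √(1/44 + 1/22) = 10.44. Noncentrality = 30 / 10.44 = 2.87. With 44 + 22 − 2 = 64 df, the noncentral t gives 80.76%, against 80.438% stated. The figure reproduces closely. It makes no use of stratification or covariates, so omitting the stratum does not lower it.

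**2. Degrees of freedom.** The planned three-arm ANCOVA has 110 − 4 = 106 residual df; with the stratum it has 105. Analytic power at SD 40 is 81.2% with either.

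**3. What each R² means in ALT units.** Between-stratum gap beyond baseline = 40 × √(R² / (p(1 − p))), where p is the proportion in one stratum.

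| R² | Gap, 55/55 split (IU/L) | Gap, 80/30 split (IU/L) |
|---|---|---|
| 1% | 8 | 9 |
| 5% | 18 | 20 |
| 10% | 25 | 28 |
| 20% | 36 | 40 |

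**4. Simulation.** 10,000 trials per setting, allocation stratified 2:2:1, one dose against placebo, least squares with treatment and baseline, without and with the stratum.

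| R² | Power without / with, 55/55 (%) | Power without / with, 80/30 (%) | Null rejection without / with, 55/55 (%) | Mean model SE without / with, 55/55 |
|---|---|---|---|---|
| 0% | 80.4 / 80.5 | 81.5 / 81.5 | 4.9 / 4.9 | 10.47 / 10.47 |
| 1% | 81.2 / 81.4 | 80.4 / 80.6 | 4.7 / 4.8 | 10.48 / 10.43 |
| 5% | 82.1 / 83.4 | 82.0 / 83.3 | 4.2 / 4.7 | 10.48 / 10.21 |
| 10% | 81.5 / 84.5 | 82.3 / 85.0 | 4.1 / 5.0 | 10.48 / 9.93 |
| 20% | 83.0 / 88.4 | 83.2 / 88.8 | 2.7 / 5.0 | 10.51 / 9.37 |

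Monte Carlo error is about 0.4 points for power and 0.2 for null rejection, which accounts for the uneven values down the columns without the stratum. The model SE is too large by 10.48/10.21 − 1 ≈ 3%, 10.48/9.93 − 1 ≈ 6% and 10.51/9.37 − 1 ≈ 12% at R² of 5%, 10% and 20%.

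**5. Mechanism check.** At R² = 20% the true spread of the estimate from the model without the stratum is 9.36, while that model reports 10.51. The model with the stratum reports 9.37. Adding the term corrects the reported standard error to what stratified randomisation already delivers.

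**6. Analytic check.** Noncentral t with SD = 40 × √(1 − R²) and 105 df gives 83.1%, 85.1% and 88.9% at R² of 5%, 10% and 20%, in line with the simulated power with the stratum.

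**7. Range for the residual SD.** If baseline ALT itself explained part of the SD of 40 (also an assumption), analytic power would be:

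| Variance explained by baseline | Without stratum (%) | With stratum, R² 5 / 10 / 20% (%) |
|---|---|---|
| 0% | 81.2 | 83.1 / 85.1 / 88.9 |
| 20% | 88.9 | 90.4 / 91.8 / 94.5 |
| 40% | 95.7 | 96.5 / 97.2 / 98.4 |

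The analytic figure without the stratum ignores the balance from stratified allocation, so these differences slightly overstate the gain. The simulated differences in step 4 are the better guide.

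**The case against.** The strongest objection concerns size. The documents give no estimate of a stratum effect, and the scenarios with a visible gain need gaps of 18 to 40 IU/L between biopsy and non-biopsy subjects beyond baseline ALT. The whole planned treatment effect is 30 and the planned placebo change is −10. SAP 8.4.2 describes both diagnostic routes with the same ALT window and the same liver-fat threshold. At an even split, a gap of 10 IU/L is a share of only 0.25 × 10² / 40² ≈ 1.6%. If baseline ALT explains much of the variance, power is already high and the gain shrinks further. All of this stands: a small gain, 0 to about 4 points, is more plausible than a large one.

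The word "initially" in SAP 3.2.1 also leaves open whether stratification was kept throughout enrolment. If it was dropped, the argument about a conservative test weakens. The remedy does not: prior biopsy is known before randomisation and remains a valid covariate.

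On the other side, the sponsor chose this factor for stratification and lists biopsy versus phenotype as a subgroup of interest. The entry routes also differ by construction (histology with fibrosis, or T2DM or pre-diabetes). Some association is plausible, though not established. None of the objections gives a reason to leave the term out.

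**Conclusion.** The point holds as a conditional efficiency improvement. The trial randomises within biopsy strata and then analyses the full population as if it had not. The treatment estimate is unbiased, type I error is not inflated and the stated power is not undermined. If the stratum explains 5%, 10% or 20% of the residual variance, the plan gives up about 1, 3 or 5–6 points of power, and its standard error is about 3%, 5–6% or 12% too large. At 0–1% nothing is lost either way. These sizes rest on the assumed share, the assumed splits and blocks, and SD 40 as the residual SD. With few placebo subjects and a nearly costless remedy, the change should be made.

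**What to change.** In SAP 8.6.1 and 8.6.2, add the randomisation stratum as recorded in the IWRS (prior liver biopsy yes/no) as a fixed effect, and not the derived diagnosis variable of SAP 8.4.2. Apply it to:

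- the primary ALT ANCOVA;
- the model fitted to each imputed dataset (SAP 7.3.1, Step 2);
- the secondary ANCOVAs on the full efficacy population.

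State in SAP 3.2.1 whether stratification applied throughout enrolment. The intensive-sampling PD models (SAP 8.8.2.2), the models restricted by diabetes status (8.6.3.6) and the Fisher's exact responder tests (8.6.3.1, 8.6.3.2) can stay as planned. The sparse PD ANCOVAs (8.8.2.1) need an explicit choice either way.

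The cost is a line of SAP text and one degree of freedom per model (106 to 105 for the primary analysis at 110 subjects). Simulated power with a non-prognostic stratum is unchanged: 80.4% versus 80.5%, and 81.5% versus 81.5%. SAP 1 already provides for logged changes before database lock and unblinding. Making the change then also avoids a post hoc choice between adjusted and unadjusted results.
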